****Updated to add changes in inclusionary criteria**

****Updated July 15, 2025 – Includes statistical analysis plan.**

Human Subjects Involvement, Characteristics, and Design

The study is a Phase I clinical trial that employs a randomized parallel design. We plan to enroll 160 children diagnosed with Developmental Language Disorder and their caregivers who will provide services to approximately half of these children. We predict that 15% of the children (N=20) will be lost to follow-up, thus we enroll 160, in order to have 140 children complete the entire study and meet the planned enrollment goals. Children will be randomly assigned to one of four treatment conditions, thus we expect 35 participants per condition. Research will be carried out at the University of Delaware and the University of Maryland College Park.

Children with Developmental Language Disorder (N = 160)

Inclusionary & Exclusionary Criteria:

- Age: 4-7 years old
- Primarily English speaking: Less than 20% exposure to another language, per parent report
- Document poor syntax skills: standard score below 85 on the DELV-NR composite, a dialect neutral assessment (Seymour, Roeper, de Villiers, & De Villiers, 2005).
- Nonverbal IQ within typical range: t-score at or above 35 on the DAS, matrices subscale, (Elliott, 2007).
- Hearing within the typical range: Pass screening using SoundScouts (Gumbie et al., 2018; Mealings et al., 2020) or provide reports of passing a hearing screening at school or in a pediatrician's office. *Due to COVID and limitations on in person activities, treatment may proceed even if these reports are not obtained if no one has concerns about hearing and we will track/follow up with families to obtain a clear hearing screening within 12 months of completion of intervention. Documentation of how many children did not complete hearing screenings will be retained and inform interpretation of data.
- No diagnosis of Autism: Cutoff score of 15 on the SCQ, (Rutter, Bailey, & Lord, 2003)
- No diagnosis of significant sensory-motor concerns or significant psychiatric disorders per parent report
- Able to benefit from treatment:
 - Score below 60% correct on experimenter developed elicited production probes of passives and object relative clauses
 - Producing simple transitive sentences (SVO) and MLU of 2.5 on 100 utterance language sample

Caregivers of Children with DLD (N=160)

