To guard against bias, children are randomly assigned to condition. A randomization scheme was pre-allocated at the beginning of the study by [name] at CRESP and uploaded to RedCap using a blinded allocation module. Allocation is requestable as children qualify for the study from CRESP. This ensures that the assessor at pre-test is blind to allocation. To ensure approximately equal allocation to each condition at each site, separate randomization schemes are used for each site. Flow through the study and drop outs at each phase are tracked following EQUATOR reporting guidelines.

Data Reduction

Estimated Dose

We compute estimated dose provided as follows:

$$\text{Dose} = \text{number of sessions reported by families} * \text{percent sessions documented based on recordings} * \text{recasts/sentences read verbatim observed in transcribed sessions}$$

Production Data

The dependent variable is production accuracy scored item by item as correct (1), incorrect (0), or unscorable (missing). Individual items are additionally coded as the syntactic type elicited (passive voice or object relative clause) and as treated/untreated clause type since that is counterbalanced across participants.

Eye-tracking Data

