Second, for each time window (early and late), we will assess the extent to which Treatment Condition affects interpretation of the treated noncanonical structure. Our dependent variable will be **Structural Sensitivity**, calculated as *an averaged difference score of Agent Preference in the canonical structure (SRC, active) minus the noncanonical structure for each structure (ORC, passive) for each child.* This measure is selected rather than Agent Preference because it captures the **degree to which a child differentiates the two structures** from each other. Sensitivity to passive/object relative clause cues will be evident in values greater than 0, with higher values mapping onto increased sensitivity. Each child will receive a single Structural Sensitivity score for active/passives and a single Structural Sensitivity score for subject/object relative clauses at each test point.

Analytic Approach

For both comprehension and production outcomes, we utilize generalized linear mixed models to examine change over time for each condition. The adoption of generalized linear mixed models (GLMM) with random effects for subjects and items as the statistical approach has advantages in that we do not need to exclude children for failing to produce scorable responses given that this model can account for uneven response rates across children (Baayen, Davidson, & Bates, 2008) and it accounts for item level variance that can affect results.

Production probe accuracy will be analyzed with a logit link function. Use of a logit link function for production data also closely mirrors the underlying data structure in which individual items are scored as correct or incorrect. Structural sensitivity will be analyzed with linear mixed-effects models. Maximal models will include random intercepts (and possibly random slopes) for subjects, items, and clause type (Barr, Levy, Scheepers, & Tily, 2013), and parameter-specific p-values will be estimated with degrees of freedom determined through Satterthwaite approximation (Luke, 2017).

We will model comprehension and production outcomes separately, though we make similar predictions as to the effect of treatment on each outcome measure. Prior to carrying out the main analyses, we will check for differences attributable to participant sex and race (relevant biological variables). These will be included in future analyses if necessary, but prior work suggests that they are not likely to influence outcomes.

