We will also use generalized additive mixed models (GAMMs) to model longitudinal patterns in eyetracking data (i.e., looks to the agent) to examine and visualize timing of stimulus effects and changes in focus at key points during and after presentation of the prompt. GAMMs model fixations as an intensive time series (Cho et al., 2018, 2022) and allow identification of key points of separation. Moreover, the GAMMs models do not require prespecification of windows of time, providing more flexibility and sensitivity when modeling differences in eyetracking over time and between groups. The specification of the GAMMs models will mirror the GLMM equations below, except that smoothing functions will be used for an additional TIME predictor to fit a spline regression for each time series.

Aim 1. Determine the relative differences in the efficacy of illustrated syntax stories and recast therapy when treatment is dose controlled and delivered by highly trained SLPs in the laboratory.

We will first confirm that we achieved control of dose in the two in-lab conditions. We will carry out an unpaired two-tailed t-test comparing the estimated dose delivered for each condition. We anticipate that the two conditions will not differ and that the distributions will show high degrees of overlap ($p>.5$, $d<.3$).

To test the key question in Aim 1, we will compare the relative effect of treatment condition by testing for differences between the treatment effect estimates of stories in the lab and recasts in the lab conditions.

Well-matched groups at pretest will be evident if the two conditions do not differ at pre-test. If one treatment condition is more effective than the other, this should be evidenced by an interaction between test point and treatment contrast effects that are significant at the p<.05 level; if, as we hypothesize, the two conditions are equally effective there will be no significant interaction between test point and treatment. We are powered to detect an effect size difference of .35 (2 raw score points) or larger on production.

$$\begin{aligned} \text{Likelihood of a Correct Production} &= \text{TestPoint} * \text{TreatmentCondition} \\ &\quad + (1|\text{item}) + (\text{clause type} |\text{subject}) \\ \text{Structural Sensitivity} &= \text{TestPoint} * \text{TreatmentCondition} \\ &\quad + (\text{clause type} |\text{subject}) \end{aligned}$$

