In the somewhat likely event that the interaction between time point and treatment is not significant, we can directly test for treatment efficacy by comparing the effect of treatment on the treated vs. untreated structures. We expect that the model estimate for Treated or Untreated clause will be significant at p<0.05 level, favoring the treated clauses, demonstrating that treatment was effective and ruling out maturational effects.

$$\begin{aligned} \text{Likelihood of a Correct Production} &= \text{TestPoint} * \text{TreatedOrUntreated} \\ &\quad + (1|\text{item}) + (\text{clause type} |\text{subject}) \\ \text{Structural Sensitivity} &= \text{TestPoint} * \text{TreatedOrUntreated} \\ &\quad + (\text{clause type} |\text{subject}) \end{aligned}$$

Aim 2. Determine whether the influence of delivery method (illustrated syntax stories or recast therapy) on dose delivered (number of exposures to the target) is of sufficient magnitude that changes in child outcomes are observed when treatment is delivered by caregivers.

We will first determine whether dose differs across the two at-home conditions. We will carry out an unpaired two-tailed t-test comparing the estimated dose delivered for each condition. We anticipate that the two conditions will differ and that the distributions will show low degrees of overlap (p<.05, d>.5).

To test the key question in Aim 2, we will test for a dose by test point or dose by treatment condition by test point interaction for stories at home and recasts at home conditions. Well-matched groups at pretest will be evident if the two conditions do not differ at pre-test. If one treatment condition is more effective than the other, this should be evidenced by an interaction between test point and treatment contrast effects that are significant at the p<.05 level; if, as we hypothesize, dose is a critical component of this difference, a two- or three-way interaction between time and dose or between time, treatment and dose will be observed. We would interpret the two-way interaction as indicating that dose, rather than treatment is critical for obtaining the key outcomes. A three- way interaction suggests that the delivery method modifies the effectiveness of the total dose.

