$$\begin{aligned} \text{Likelihood of a Correct Production} &= \text{TestPoint} * \text{TreatmentCondition} * \text{EstimatedDose} \\ &\quad + (1|\text{item}) + (\text{clause type} |\text{subject}) \\ \text{Structural Sensitivity} &= \text{TestPoint} * \text{TreatmentCondition} * \text{EstimatedDose} \\ &\quad + (\text{clause type} |\text{subject}) \end{aligned}$$

In the event that the interaction between time point and treatment is not significant, we can directly test for treatment efficacy by comparing the effect of treatment on the treated or untreated structures. We expect that the model estimate for Treated vs. Untreated clause will be significant at p<0.05 level, favoring the treated clauses, demonstrating that treatment was effective and ruling out maturational effects.

$$\begin{aligned} \text{Likelihood of a Correct Production} &= \text{TestPoint} * \text{TreatedOrUntreated} \\ &\quad + (1|\text{item}) + (\text{clause type} |\text{subject}) \\ \text{Structural Sensitivity} &= \text{TestPoint} * \text{TreatedOrUntreated} \\ &\quad + (\text{clause type} |\text{subject}) \end{aligned}$$

Power Analysis for Production

Power analyses were carried out using Monte Carlo simulation (5,000 iterations) via SAS 9.4 and PROC GLIMMIX using residual pseudolikelihood estimation of a binary logistic mixed effects model with item responses (n=20) nested within tests (n=4 representing test point and clause type repeated measures) that are nested within children (n=120) who have been randomly assigned to treatment conditions, counterbalanced across the 2 clauses. Random effects are included for items within clauses, as well as four correlated child-level random effects (i.e., for each of the four repeated measures). A single model was used to estimate power in alignment with the overall design of the study in which children are randomly assigned to one of FOUR conditions. Power for the more focused models described above can be inferred from the power estimates for the treatment contrasts below. By adopting this randomization scheme and model design, we retain the ability to test unplanned contrasts that go beyond the planned analyses for the Aims if we so chose (e.g., recasts in the lab vs. recasts at home) in order to carry out secondary analysis associated with cost effectiveness, dose, or home environment.

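### Allocation is stratified by site, but the between-arm models for Aims 1 and 2 and the GAMMs that mirror them have no site term: a small loss in the randomised comparison, a possible confounder of dose in Aim 2

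*Protocol*

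**What the plan says.** The opening design section names two sites: "Research will be carried out at the University of Delaware and the University of Maryland College Park". On size it states: "Children will be randomly assigned to one of four treatment conditions, thus we expect 35 participants per condition". Under Statistical Design and Power, Randomization, the protocol says that "separate randomization schemes are used for each site", and gives the reason: to keep the numbers in each condition roughly equal within each site.

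The Aim 1 and Aim 2 sections then write out eight model formulas, four for production and four for Structural Sensitivity.

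| Models | Fixed effects | Site? |
|---|---|---|
| Aim 1, between arms (2) | test point x treatment condition | no |
| Aim 2, between arms (2) | test point x treatment condition x estimated dose | no |
| Aims 1 and 2, fallback (4) | test point x treated-or-untreated clause | no |

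The random part is clause type within subject, plus an item intercept for production. On random effects, Analytic Approach says "Maximal models will include random intercepts (and possibly random slopes) for subjects, items, and clause type", and site is not among them. The only further covariates considered are sex and race, to be added if needed. The GAMMs are to follow the same equations with a smooth of time added. The simulation in Power Analysis for Production nests items in tests in children and has no site level. No reason for leaving site out is given, and no site-adjusted sensitivity analysis is planned.

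**The concern.** A factor important enough to balance at randomisation normally belongs in the analysis. The key test in both aims concerns change from pre- to post-test. A child intercept absorbs a site difference in level, but no term in the written formulas absorbs a site difference in gain. Such a difference is plausible in the lab arms, where each site has its own staff, and possible in the home arms through caregiver training or local recruitment.

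Two things are at stake. First, Aim 1 reads a non-significant interaction as support for its hypothesis that the two lab conditions are equally effective, so any avoidable loss of power leans towards the expected answer. Second, Aim 2 interprets a dose-by-test-point interaction as evidence that dose, rather than treatment, matters. Estimated dose is built from reported sessions, recordings and transcribed delivery. It is observed, not assigned, so stratified allocation does not protect that term.

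**Working it through.** The protocol states no figure for site, so there is none to reproduce. All site differences below are assumptions.

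**1. Linear model (Structural Sensitivity).** Inputs: 30 children per arm (the 120 of the power analysis over four arms), two equal sites, arms balanced within site, two-sided 0.05. Assumed: an arm difference of 0.7 SD in change and a site difference of d SD in change. One change score per child stands in for the planned mixed model.

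Omitting site adds d²/4 to the residual variance. Site's share of the variance of change is (d²/4)/(1 + d²/4), and the estimated standard error grows by √(1 + d²/4).

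- d = 0.25: share 1.5%, standard error x 1.008
- d = 0.5: share 5.9%, standard error x 1.031
- d = 1.0: share 20%, standard error x 1.118

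Because the arms are balanced within site, the site effect cancels from the arm difference. The estimate's true variability does not grow while its estimated standard error does, so the test is conservative. With site in the model, the noncentrality is 0.7/√(2/30) = 2.71 on 57 df, which gives power 0.76. Simulation with 20,000 runs per setting:

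| Site difference (SD) | Type I error, no site | Type I error, site | Power, no site | Power, site |
|---|---|---|---|---|
| 0 | 0.051 | 0.050 | 0.76 | 0.76 |
| 0.25 | 0.046 | 0.047 | 0.76 | 0.76 |
| 0.5 | 0.043 | 0.049 | 0.74 | 0.77 |
| 0.8 | 0.032 | 0.049 | 0.71 | 0.76 |
| 1.0 | 0.029 | 0.049 | 0.68 | 0.76 |

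The last column varies only by simulation error. The mean estimated arm difference was about 0.70 in every power run, with or without site, so there is no bias. With 34 per arm, close to the planned 35, the pattern is the same: power 0.79 against 0.81 at 0.5 SD.

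**2. Logit model (production).** Item-level binary data have no free residual variance, and the written formula has no by-child slope for test point. A simplified random-intercept logistic simulation used 60 children, 20 items at each of two test points, an assumed SD of 0.6 logits for child gain, no arm effect and 250 runs per setting. The mean standard error of the interaction was:

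- site difference 0.5 SD: 0.209 without site, 0.210 with it
- site difference 1 SD: 0.210 without site, 0.211 with it

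The site terms bring no gain in precision. What remains is attenuation, approximately 1/√(1 + 0.346 g²/4) for a site difference of g logits, where 0.346 = (16√3/15π)² is the usual logistic-normal constant. For g = 0.5 x 0.6 = 0.3 the factor is 0.996. For g = 0.6 it is 0.985.

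**3. Dose in Aim 2.** Illustration: 70 home-arm children (2 x 35), two equal sites that differ by d SD in both dose and gain, no true dose effect, simple correlation of dose with gain. The spurious correlation is r = (d²/4)/(1 + d²/4). The chance of a false positive follows from Fisher's transformation, with shift atanh(r) x √67.

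- d = 0.5: r = 0.059, shift 0.48, false positives about 8%
- d = 1.0: r = 0.20, shift 1.66, false positives about 38%

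**4. Treated-versus-untreated models.** Each child contributes both clause types, so this contrast is within child. Site and Site x TestPoint move both clauses alike and leave it essentially unchanged.

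**The case against.** The best case for leaving the models alone is that the harm is small and unproven. The protocol gives no site difference, the loss in step 1 is about two power points at 0.5 SD, and that simulation uses change scores rather than the planned mixed models. For production, the site terms do not tighten the standard error at all. All of this stands, and it limits the point to a modest one.

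A reader might infer several stronger things that the protocol does not support.

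- **That the arm comparison is biased or its type I error inflated by omitting site.** Allocation is balanced within site. The linear estimate is unbiased and the error moves downward.
- **That every model loses precision.** This is linear-model reasoning. It fits Structural Sensitivity, but not production as written. It would return for production if a by-child test-point slope were added, which Analytic Approach leaves open. In the logistic simulation, null rejection was .092 without site and .100 with it at 0.5 SD, and .112 either way at 1 SD. That excess comes from the missing slope, a separate matter that site terms do not cure.
- **That dropout leaves a site imbalance uncorrected.** This would need dropout that differs jointly by arm and site. The protocol anticipates only an overall 15%.
- **That all eight formulas need repair.** The four within-child models do not.

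The omission cannot be put down to detail left for a later plan. The protocol's header says that it includes the statistical analysis plan, and the models are fixed term by term.

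**Conclusion.** The point holds in modest form. Site defines the randomisation strata and is absent from all four between-arm formulas and the GAMMs that mirror them.

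- **Randomised contrast:** no bias. For Structural Sensitivity the test is somewhat conservative if sites differ in gain (power about 0.76 to 0.74 at 0.5 SD, 0.68 at 1 SD, negligible at 0.25 SD or less). For production, attenuation is under 2% even at an assumed 0.6 logits.
- **Aim 2 dose term:** confounding by site is possible, because dose is not randomised. It requires sites to differ in both dose and gain. The 8% and 38% are illustrations from a simple correlation, not forecasts for the planned model.

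These sizes assume two equal sites and the site differences named, none of which come from the protocol. The case for change is that the remedy is nearly free, not that the trial's conclusions are in danger.

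**What to change.** Add Site and Site x TestPoint as fixed effects to the Aim 1 (test point x condition) and Aim 2 (test point x condition x estimated dose) models, for both production and Structural Sensitivity, and to the matching GAMMs. Two sites are too few for a random effect. The interaction is needed because the tests concern change, and a main effect of site alone would not act on it. Leave the treated-versus-untreated models as they are.

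If the unadjusted models are kept as primary, state the reason and prespecify a site-adjusted sensitivity analysis before outcomes are analysed. The cost is two extra parameters per model and a line of wording. Site is already known for every child, so no new data are needed.

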Eye-movements are continuously sampled at the rate of 500 Hz (every 2 ms) from trial onset to the onset of the pointing prompt. Fixations are coded as present (looks to an area of interest on screen) or missing (looks away from these interest areas, track loss, blinking). Present looks are recoded as Agent fixations or Patient fixations based on the looks' relation to target sentences. "Agent fixations" are looks to areas of interest where first-mentioned noun phrases are agents (i.e., correct interpretation for actives and subject relative clauses). "Patient fixations" are looks to areas of interest where first-mentioned noun phrases are patients (i.e., correct interpretation for passives and object relative clauses). Based on pilot data, linguistically mediated eye-movements in responses to the speech stream occur primarily during a 2-second window from the disambiguating verb morphology. Also, consistent with prior work (Huang et al., 2013; Huang et al., 2017), our pilot data indicate that interpretations of canonical structures (i.e., actives) occur faster than noncanonical structures (i.e., passives). On this basis, we will run separate analyses over an "early window" (e.g., first 1000 ms after disambiguation) and "late window" (e.g., second 1000 ms after disambiguation). To examine sensitivity to the timing of window transitions, and to better pinpoint typical timing of stimulus effects, we will explore a range of time values distinguishing potential early and late windows.

Within these windows, we will first calculate **Agent Preference** for each item and then use this value to derive **Structural Sensitivity** for each set of sentences (active/passive, subject/object relative clause). First, for each test point (pre- and post-) and sentence type, we will determine whether canonical and noncanonical structures elicit different interpretations. **Agent Preference** will be calculated as an averaged proportion of Agent looks over Agent plus Patient looks. Values greater than 0.5 indicate a preference to look at the Agent while values less than 0.5 indicate a preference for the Patient.

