Simulations that include dose indicate power of .93 for models that include dose and time. Effects of treatment, dose, and power combined are not detectable because this estimation of dose confounds the distribution of dose with treatment delivery approach, as we hypothesize in the strategy. It suggests that three-way interactions will only be detectable if the delivery method modifies the benefit obtained from each exposure to the target form.

Power Analysis for Eye Tracking

Power analyses were carried out using G*Power (Faul, Erdfelder, Lang, & Buchner, 2007). Our preliminary data focused on eye-movements during a single test point, thus we do not have relevant estimates of fixation changes at multiple time points or following interventions. Consequently, we based our sample size on power analyses for production ($n=120$) and calculated the smallest changes in Structural Sensitivity that will be detectable with varying levels of power.

In our preliminary data ($n=15$), children with DLD revealed $M = 0.02$ and $SD = 0.17$ in the late window. With the proposed sample size, effect sizes of $d=.30$ will be detectable with 80% power, $d=.34$ with 90% power, and $d=.42$ with 99% power. These correspond to increases in Structural Sensitivity of $M=.05$, $M = .06$, and $M = .07$ respectively. For reference the TD children in our Preliminary Data have a Structural Sensitivity score that is $M=.29$ larger than that of the children with DLD. Based on this benchmark, improvements across time points that are 17-24% in magnitude would be detectable in the current design. This suggests that this study is adequately powered to detect relatively small changes in linguistically mediated fixations.

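### Comprehension is tested in an early and a late eye-tracking window with example-only limits, no primary window and no rule for disagreement; if either may answer the aim, the false-positive chance per contrast is about 7-9.75%, not 5%

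*Protocol*

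**What the plan says.** All references are to the protocol, whose opening note says this version includes the statistical analysis plan.

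- **Data Reduction, Eye-tracking Data (span).** Pilot data are cited to show that language-driven eye movements "occur primarily during a 2-second window from the disambiguating verb morphology".
- **Same section (windows).** Within that span, "we will run separate analyses over an 'early window' (e.g., first 1000 ms after disambiguation"), and the other is the "late window' (e.g., second 1000 ms after disambiguation"). Both limits are examples.
- **Same section (boundary).** The purpose of varying the split is given: "To examine sensitivity to the timing of window transitions, and to better pinpoint typical timing of stimulus effects". Then: "we will explore a range of time values distinguishing potential early and late windows". No limits or step size are stated.
- **Same section (outcome).** The effect of treatment condition is to be assessed in each of the two windows. The paragraph ends: "Each child will receive a single Structural Sensitivity score for active/passives", with a matching score for relative clauses, at each test point.
- **Analytic Approach, Aims 1 and 2.** The model formulas contain one Structural Sensitivity outcome with no window index. If one treatment is more effective, "this should be evidenced by an interaction between test point and treatment contrast effects that are significant at the p<.05 level". If the interaction is not significant, both aims go on to compare treated with untreated structures.
- **Analytic Approach, GAMMs.** A window-free time-course analysis is added, with no stated rank relative to the window tests.
- **Power Analysis for Eye Tracking.** The sample size is taken from the production outcome (n=120). Detectable effects are put into raw units with pilot figures: "children with DLD revealed $M = 0.02$ and $SD = 0.17$ in the late window".

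**The concern.** An analyst following the text obtains at least two p-values for each comprehension contrast, each judged at .05, and cannot tell which one answers the aim. Three things follow.

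1. If either window may count, the error rate for the comprehension conclusion exceeds 5%.
2. The next analytic step depends on whether the interaction is significant. If one window is significant and the other is not, the plan does not say whether that step applies.
3. Aim 1 predicts no significant interaction. With two unranked windows that disagree, one could be cited for a difference and the other for equal effectiveness, from the same data.

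The movable boundary adds to this. A sensitivity analysis needs a fixed reference analysis, and here the 1000 ms split that would serve as the reference is itself only an example.

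**Working it through.** **Inputs from the protocol.** Per-test criterion .05 (Aims 1 and 2); two windows in a 2-second span, with an example split at 1000 ms (Eye-tracking Data); N=120, SD .17, and d = .30, .34 and .42 at 80%, 90% and 99% power (Power Analysis for Eye Tracking); four conditions.

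**Assumed, because the protocol does not give them.** The correlation between early and late test statistics; the range and step of the boundaries; the autocorrelation of looks over time; the pre-post correlation in the power check.

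**Step 1: the plan's own eye-tracking figures.** The G*Power test is not named. A repeated-measures within-between interaction F test with 4 groups, 2 measurements, f = d/2 and assumed correlation .5 has noncentrality f² × N × 2/(1 − .5). At d=.30 this is .15² × 120 × 4 = 10.8, on 3 and 116 degrees of freedom.

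| d | Stated power | Recomputed | d × .17 |
|---|---|---|---|
| .30 | .80 | .781 | .051 |
| .34 | .90 | .882 | .058 |
| .42 | .99 | .978 | .071 |

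Each power is within 2 points. The raw changes round to the stated .05, .06 and .07, and .05/.29 = 17% and .07/.29 = 24% also match. These figures are for one test at .05.

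**Step 2: two fixed windows, either may count.** If independent, 1 − (1 − .05)² = .0975. If correlated, the chance that at least one of two jointly normal statistics exceeds 1.96 in absolute value is:

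| Correlation | Chance | Multiple of 5% |
|---|---|---|
| 0 | 9.75% | 1.95 |
| .5 | 9.1% | 1.8 |
| .8 | 7.8% | 1.6 |
| .9 | 7.0% | 1.4 |

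The multiple stays below 2 throughout.

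**Step 3: boundary also chosen on results.** This was simulated with 100,000 null draws per setting of the treatment-by-test-point statistic in 50 ms bins over 2 s. Autocorrelation was exponential (50-800 ms) with a shared child component (0-0.5). Any significant result, in either window at any boundary tried, counts. Steps are 100 ms unless noted.

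| Assumed boundary range | Chance of a false result |
|---|---|
| 800-1200 ms | 8.2-16.8% |
| 600-1400 ms | 9.7-22.4% |
| 400-1600 ms | 11.0-27.6% |
| 200-1800 ms, 50 ms steps | 13.1-35.4% |

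At moderate settings (600-1400 ms, autocorrelation 200-800 ms, shared component .1-.25) the chance is 12.1-16.6%. If only the late window counted but its boundary were searched over 600-1400 ms, it is 6.7-12.3% across all settings.

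**Step 4: after the fix.** One fixed window gives 5% per contrast. Two fixed windows at .025 each give at most 5% (1 − .975² = 4.94% if independent). Under the F test of Step 1, power at d=.30 then falls from .78 to .69, and the effect detectable with 80% power rises from about .31 to about .34.

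**The case against.** The strongest reply is that the boundary search is not a search for significance. Its sentence opens with a stated purpose, a check on window timing and on when stimulus effects occur, and nothing says that the smallest p-value decides the aim. That stands. A reader might infer that a false treatment effect is two to three times as likely as nominal. The documents do not support that as a general statement: it needs an assumed boundary range, assumed autocorrelation and a best-result rule that the protocol does not contain. The two windows to which the text commits give less than twice 5%. The protocol also states .05 per test and claims no family-wise rate.

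Three other strong readings also fail.

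- *No measurement window is fixed at all.* The 2-second span is set in advance from pilot data; only the split within it is open.
- *The single-score sentence contradicts the two windows.* Its paragraph opens by distinguishing the windows, so it can be read as one score per window. The wording is loose and needs clarifying, but it is not a proven contradiction.
- *The study was sized on the late window.* It was sized on production. The late-window SD only converts d into raw units.

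It can also be said that choosing a significant window would go against the investigators' own Aim 1 prediction. That weakens any suggestion of motive, but it does not supply a decision rule.

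Setting all of this aside leaves two unranked windows, example-only limits and a fallback with no defined trigger. Leaving these to a later analysis plan is a weak answer, since the document says it includes that plan and already gives formulas, a degrees-of-freedom method and a significance criterion.

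**Conclusion.** The concern holds in this form. The comprehension outcome is tested in two windows with no primary window, no exact limits and no rule for disagreement. If either window may answer the aim, the false-positive chance per contrast is about 7-9.75% against a nominal 5%, for between-window correlations of .9 down to 0.

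A figure of roughly 12-17% applies only if the boundary is also selected on results, under moderate assumed settings. The protocol gives no boundary range and does not describe the search that way, so this figure is conditional and not a property of the plan.

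All figures refer to one treatment-by-test-point contrast. Aim 2's dose interactions were not simulated, and its choice between a two-way and a three-way interaction is not counted. The undefined fallback in both aims does not depend on any of these assumptions.

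**What to change.** - In Eye-tracking Data, replace the example limits with exact ones, for instance 0-1000 ms and 1000-2000 ms after disambiguation.
- Name one window as the comprehension outcome for Aims 1 and 2, and write it into the Structural Sensitivity formulas. The late window is the natural choice because the detectable effects already use its SD. Make the other window secondary. Alternatively, test both at .025 each.
- State that the named window (or the split-alpha rule) decides whether the comparison of treated with untreated structures applies.
- Label the moved boundaries and the GAMMs as sensitivity or exploratory analyses with no bearing on whether an aim is met.
- Reword the single-score sentence to one score per structure, window and test point.

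**Cost.** A few sentences and no new data. With the late window named, an effect confined to the early window could be reported only as secondary. Splitting alpha avoids that, at the price of the power loss shown in Step 4 of the working.
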